Oxytocin is a neuropeptide known to have prominent anxiolytic and prosocial effects. Among both animals and humans, oxytocin is known to mitigate the effects of social stress on addictive behaviors. Among normative couples, preliminary data suggests that oxytocin promotes more positive conflict resolution skills. Taken together, this literature suggests that oxytocin holds promise as a tool to modulate the effects of dyadic conflict on addictive behaviors. If evidence supporting this notion emerged, these data would support the investigation of oxytocin as a potential augmenter to couples therapies for substance abuse problems. However, the first step toward evaluating oxytocin in this role, and the primary objective of the proposed study, is to examine the extent to which oxytocin improves conflict resolution skills among couples with substance abuse. Our secondary objective is to examine the extent to which oxytocin mitigates couples' subjective, physiological, and neuroendocrine reactivity to dyadic conflict. Thirty-six couples (n=72) consisting of at least one partner with recent substance abuse will participate in the study. The study will consist of one 4-hour laboratory visit. Couples will complete a thorough psychosocial assessment interview and two 10-minute videotaped conflict resolution tasks using a well-established paradigm. Participants will be randomly assigned to self-administer either a 40 IU dose of intranasal oxytocin or placebo. We will implement a double-blind design. We will examine standardized, repeated dependent measures of change in each partner's conflict resolution skills, subjective, physiological, and neuroendocrine responses to the conflict resolution task. The following specific aims are proposed:

Specific Aim 1: Examine the effects of oxytocin on couples' conflict resolution skills.

Couples will complete a psychosocial assessment and two 10-minute videotaped conflict resolution tasks. 45 minutes prior to the second conflict resolution task, a 40-IU dose of intranasal oxytocin or saline spray will be administered to both partners. Conflict resolution skills will be coded according to a well-established system and compared from Task 1 to Task 2.

Specific Aim 2: Examine the effects of oxytocin on couples' subjective, physiological, and neuroendocrine reactivity to the conflict resolution task.

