In addition, [name] is serving as a co-mentor and co-investigator on the proposed project. [name] is Professor and Director of Clinical Training at Ryerson University. [name] previously served as Deputy Director of the Women's Health Sciences Division at the National Center for PTSD in Boston as has an extensive research track record including serving as PI on several VA and NIH funded treatment development research studies focusing on designing couples therapies. [name] combination of expertise in couples therapy treatment development, women's health, and Veterans health is an ideal compliment to [name] mentorship team.

4. RESEARCH DESIGN AND METHODS (including data analysis)

A. Overview

The primary objective of this study is to examine the extent to which oxytocin improves couples' conflict resolution skills and mitigates their subjective, physiological, and neuroendocrine responses to this common stressor. Couples in which one or both partners have a recent history of substance abuse will be recruited. The present study will take place over one visit. In addition to a thorough psychosocial evaluation conducted by a trained clinician, couples will complete two laboratory conflict resolution tasks. Prior to the start of the second conflict resolution task, both partners will be administered a 40 IU dose of intranasal oxytocin. The flow chart below illustrates each element of the study:

B. Subjects

Thirty-six couples (N=72 individuals total) will be recruited to participate in the proposed study. Respondents will be screened by phone and provided all pertinent information about the study. Inclusion criteria are: 1) 18-65 years of age, 2) both partners are willing to participate, and 3) at least one partner has engaged in hazardous drinking (i.e. 4 or more drinks for women, 6 or more for men) or illicit drug use during the past 60 days. Exclusion criteria are: 1) pregnancy for women, 2) current psychotic or bipolar disorders, 3) active suicidal or homicidal ideation and intent, 4) subjects who would

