Expertise of Research Team. The PI, her mentor, co-mentor, and consulting staff at MUSC were assembled for the specific purpose of the proposed study. Each investigator taking part in this project has expertise in the treatment of PTSD, SUDs, and interpersonal violence. [name] also has expertise in the assessment and treatment of couples and the administration of behavioral interventions for couples in a variety of treatment settings.

Use of multi-modal, longitudinal assessments. The combined use of self-report, interview, observational, physiological, and dyadic data will provide rich and highly informative data. The repeated measures design of this study (assessing the same constructs over multiple assessment time points) will allow the research team maximize construct validity and evaluate a wide range of potential outcome variables in order to derive the most information possible from these data.

Assessment of novel treatment approach. Oxytocin has demonstrated tremendous promise in the fields of addiction. The present study is one of the first to investigate the effects of oxytocin on couples conflict resolution skills. It is the first to examine its effect on dyadic conflict resolution among couples with substance abuse problems, and the first to examine its effects on subjective, physiological, and neuroendocrine correlates dyadic conflict.

I. Limitations of study design

Use of retrospective self-report data. Recall bias may be a factor that limits the validity and generalizability of the proposed study. The use of multi-model assessment approaches may minimize the limitations incurred by this design element.

Absence of control group. A more rigorous design may include a control group receiving placebo with which to compare a treatment group. However, the goal of this preliminary study is to evaluate the feasibility and preliminary efficacy of oxytocin on the above mentioned factors and to provide information that will facilitate its revision and improvement.

J. Project timeline

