During the first 3 months of this project, 2-3 couples will be recruited to pilot the study procedures. Also during this time, the study database will be created and data entry will be ongoing. Following the completion of this pilot phase, recruitment and assessment of couples will continue. Data cleaning and maintenance will also begin in month 4 and will continue through the duration of the study. Dissemination of data including presentation of preliminary pilot data at national conferences will begin in the second year of the project.

K. Study personnel

Principal Investigator: [name]. is an Assistant Professor within the Department of Psychiatry and the Division of Clinical Neurosciences at MUSC. [name] is a clinical psychologist with 10 years of specialized training in the treatment of trauma, substance abuse, and interpersonal violence. [name] received her Ph.D. from the University of Tennessee, completed her internship at the VAMC Puget Sound, Seattle, and a postdoctoral fellowship in the NIDA-funded T32 training program within the Department of Psychiatry at Yale University School of Medicine. She was the PI of a NIAAA-funded NRSA entitled Risk Factors for Intimate Partner Violence During Pregnancy. She is currently serving as Co-Investigator on a NIDA-funded study aimed at evaluating the efficacy of an integrated treatment for PTSD and substance abuse among OIF/OEF Veterans (PI; [name]). She also has extensive experience working with diverse and vulnerable populations (e.g., pregnant women, incarcerated and court-mandated individuals, individuals with substance use disorders). Across various studies, she has taken a lead role in developing and implementing recruitment protocols; hiring, training and supervising research staff; designing and maintaining stringent human subjects protection plans; conducting statistical analyses; and preparing data for conference presentation and submission to peer-reviewed journals. She has expertise in mental health treatment, including dyadic interventions among civilian and military populations to address PTSD and co-occurring problems such as substance abuse and interpersonal violence.

Co-Investigator: [name]. is an Associate Professor in the Department of Psychiatry at the Medical University of South Carolina (MUSC), and a clinical psychologist specializing in substance use disorders (SUDs) and the integrative treatment of co-occurring PTSD. She is a Staff

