6. PROTECTION OF HUMAN SUBJECTS

Risks to the subjects. The PI and co-investigators located at MUSC have completed the mandatory University of Miami CITI Human Subjects Research Education Course online. All research activities will be reviewed by MUSC's IRB on a yearly basis. The research staff will ensure that all information needed for the continuing review is at the IRB in accordance with IRB requirements.

Human Subjects Involvement and Characteristics. A total of 30 couples (60 individuals) who meet inclusion criteria will be enrolled in the proposed study over a 2 year period. Women and men of all racial and ethnic groups are eligible for participation in the proposed study. Charleston's population is 64% Caucasian, 34% African American and 2% identifying a racial background other than those previously listed. Therefore we anticipate a similar racial spectrum for the proposed study. Individuals under the age of 18 will not be included in the study. Inclusion criteria dictate that all participants must be 18-65 years of age, both partners must be willing to participate, at least one partner in the couple must endorse substance abuse in the past 60 days. Exclusion criteria include pregnancy for women, current psychotic or bipolar disorders, active suicidal or homicidal ideation and intent, subjects who would present a serious suicide risk, such as those with severe depression, or who are likely to require hospitalization during the course of the study, severe unilateral IPV in the past year, or BMI greater than 39. If both partners meet criteria for participation and independently provide informed consent, they will be scheduled to complete a baseline assessment.

Targeted/Planned Enrollment Table

Total Planned Enrollment: 40

TARGETED/PLANNED ENROLLMENT: Number of Subjects			
Ethnic Category	Sex/Gender		
	Females	Males	Total
Hispanic or Latino	0	0	0
Not Hispanic or Latino	36	36	72
Ethnic Category: Total of All Subjects*	72		

Racial Categories			
American Indian/Alaska Native	0	0	0
Asian	0	0	0
Native Hawaiian or Other Pacific Islander	0	0	0
Black or African American	24	24	48
White	12	12	24
Racial Categories: Total of All Subjects*	36	36	72

*The "Ethnic Category: Total of All Subjects" must be equal to the "Racial Categories: Total of All Subjects".

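### The planned sample size is stated as 36 couples (72 people), 30 couples (60 people) and 40, and nothing in the available text says which governs

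*Combined protocol and SAP*

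**What the plan says.** Section 1 (Specific Aim): "Thirty-six couples (n=72) consisting of at least one partner with recent substance abuse will participate in the study".

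Section 4.B (Subjects): "Thirty-six couples (N=72 individuals total) will be recruited to participate in the proposed study".

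Section 6 (Human Subjects Involvement and Characteristics) has this sentence: "A total of 30 couples (60 individuals) who meet inclusion criteria will be enrolled in the proposed study over a 2 year period".

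The Targeted/Planned Enrollment Table follows in the same section. Its heading reads "Total Planned Enrollment: 40". Its label reads "TARGETED/PLANNED ENROLLMENT: Number of Subjects", and its cells give 36 females and 36 males, 72 in total.

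Section 4.J adds that in the first three months "2-3 couples will be recruited to pilot the study procedures". It does not say whether these couples count towards the target.

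**The concern.** The enrolment target fixes when recruitment ends, and it is the denominator for reporting retention and disposition. Here the study could close at 30 or at 36 couples and match a stated target either way. The section that sets out participant protection describes, in its prose, 12 fewer people than the aims and methods intend to study. It also disagrees with the table printed beneath it, and that table's heading disagrees with its own cells.

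**Working it through.** **Inputs**

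| Place | Couples | Individuals |
|---|---|---|
| Section 1 | 36 | 72 |
| Section 4.B | 36 | 72 |
| Section 6, prose | 30 | 60 |
| Section 6, table cells | 36 (inferred from 36 women and 36 men) | 72 |
| Section 6, table heading | not stated | 40 (the line has no unit; the table label says subjects) |

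**Each figure on its own terms.** 36 × 2 = 72 and 30 × 2 = 60, so both couple/individual pairs are right. In the table, ethnicity gives 36 + 36 = 72, race gives 48 + 24 = 72, and each sex gives 24 + 12 = 36. The cells are intact, and the discrepancy is not a broken table.

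**Between the figures**

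- 72 − 60 = 12 people; 12/72 = 16.7%.
- Heading read as subjects: 40/2 = 20 couples; 72 − 40 = 32 people; 32/72 = 44.4%.
- Heading read as couples: 40 × 2 = 80 people, 8 more than 72 and 20 more than 60.

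Neither reading of 40 matches 60 or 72.

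**Possible reconciliations**

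- *Pilot couples.* 36 − 2 = 34 and 36 − 3 = 33. Neither is 30.
- *Dropout from 36 to 30.* Solving 30/(1 − d) = 36 gives d = 1 − 30/36 = 16.7%. If the result was rounded up to 36, any d above 1 − 30/35 = 14.3% would also do. No such rate is stated, and the 30 couples are described as enrolled, not as completing.
- *Dropout from 40 to 36, in couples.* 36/(1 − 0.10) = 40, so a 10% allowance would link these two. No such allowance is stated, section 4.B describes the 36 as recruited, and 40 couples would be 80 subjects in a table whose cells total 72.
- *Recruited versus enrolled.* Section 1 says that 36 couples will take part, which cannot exceed the number enrolled. The planned-enrolment table also totals 72, directly below prose that gives 60.

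**Effect on precision.** With design, allocation and analysis held fixed, the standard error scales as 1/√(couples). The ratio for 30 against 36 is √(36/30) = 1.095, or about 9.5% wider.

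No detectable effect is given. The available text supplies no standard deviation, within-couple correlation or allocation ratio. It also conflicts on the comparison itself: section 1 randomises to oxytocin or placebo, while section 4.I lists "Absence of control group" as a limitation.

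**The table as evidence for 36.** The text above the table says that the local "population is 64% Caucasian, 34% African American" and expects a similar mix. The table has 24/72 = 33.3% White and 48/72 = 66.7% Black, roughly the reverse. Applied to 72 people, the stated mix would give 0.64 × 72 = 46.1 and 0.34 × 72 = 24.5. The total of 72 is unaffected, but the table may not have been checked closely.

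**The case against.** The strongest reply is that this is a text-alignment slip with little practical effect. The figure of 36 couples stands in the aims and in the methods section that staff would use to run the study, and the table cells agree with it. The figures 30 and 40 appear once each, both in section 6. The study calls itself preliminary and, in the available text, gives no power or precision target, so the wider standard error breaches nothing stated. An early stop at 30 couples is a possibility, not something the documents show.

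Much of this is fair, and it limits how serious the point is. The 44.4% gap also depends on reading 40 as subjects. The table label supports that reading, but the heading line itself carries no unit. None of this removes the contradiction. A sample size is a figure that the trial relies on, and the available text does not say which one governs.

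Text between sections 4.K and 6 is absent from the copy reviewed, so a justification may exist there. Even so, sections 1, 4.B and 6 as printed would still disagree.

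**Conclusion.** The concern holds. Sections 1 and 4.B and the table cells plan 36 couples (72 people), the section 6 prose plans 30 couples (60 people), and the table heading says 40. Moving from 36 to 30 couples costs 12 people (16.7%) and widens the standard error by about 9.5%, assuming the same design, allocation and analysis. This is an inconsistency between stated targets. It is not a failed power calculation, and neither 30 nor 36 is judged inadequate. It should be corrected. The documents do not settle which figure was intended, though 36/72 is the one that recurs.

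**What to change.** State one target everywhere, in couples and in individuals.

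- **If 36 couples and 72 individuals is intended** (the default, since the aims, methods and table cells agree on it), correct the sentence giving 30 couples and the heading giving 40, both in section 6. Sections 1 and 4.B do not change.
- **If 30 couples is intended,** change sections 1 and 4.B, the table cells and the heading instead.
- **In either case,** say whether the target means couples recruited, enrolled or completing, and whether the pilot couples count. While the table is open, check its race rows against the sentence above it.

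Notify the ethics board of the correction. The available text does not show which figure the board holds. Section 6 (Regulatory Issues) also commits to reporting protocol changes to the funder.

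If 36 is kept, the cost is a short text edit, almost all of it in section 6, and a notice. The design and analysis are untouched.

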The experienced research staff conducting this study will make every possible effort to maintain the safety of our research participants, to minimize the risks and burden they incur as a result of participation, and to maximize potential benefits. The knowledge we may gain from the proposed study will address a crucial need for studies to develop and evaluate treatments to improve the health of couples. In the event that new information regarding the risk to benefit ratio becomes available during the course of the study, research participants will be notified. Further, the PI and her mentor will consult with our research team and DSMB to make any necessary study modifications.

Data and Safety Monitoring Plan

This section is based on the recommendations in NIDA's "Guidelines for Developing a Data and Safety Monitoring Plan" (www.drugabuse.gov/funding/dsmb.html).

Summary of the Protocol. The proposed study aims to develop and conduct initial feasibility and efficacy testing of oxytocin for the improvement of couples' conflict resolution skills. The primary outcome in this study includes an improvement in conflict resolution skills and a reduction in subjective, physiological, and neuroendocrine reactivity to dyadic conflict.

Trial Management. The study will be managed from the Division of Clinical Neuroscience within the Department of Psychiatry and Behavioral Sciences at the Medical University of South Carolina.

Data Management and Analysis. A data analytic plan is outlined in the Data Analysis section. Because this study is a preliminary test of a new medication, we are interested in examining a broad range of outcome variables. The main outcome variables include the frequency and severity of negative conflict resolution skills and the frequency and intensity of positive conflict resolution skills as well as

subjective, physiological, and neuroendocrine reactivity to dyadic conflict. Outcome data will be analyzed using regression analyses, structural equation modeling, and hierarchical linear modeling. The alpha level for statistical significance will be set at .05.

Quality Assurance. Data quality will be monitored by random inspection of completed assessment forms by research staff. Any problems with the assessment process, data collection, or data entry will be discussed with the PI and [name].

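### The plan ranks reactivity as secondary in one section and as primary in two others, and does not fix the skills score, so the primary claim could be chosen after the data are seen

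*Combined protocol and SAP*

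**What the plan says.** Three places state the main objective or outcome.

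- Section 1, Specific Aim, says that the "primary objective of the proposed study, is to examine the extent to which oxytocin improves conflict resolution skills among couples with substance abuse". It continues: "Our secondary objective is to examine the extent to which oxytocin mitigates", and what follows is the subjective, physiological and neuroendocrine reactivity.
- Section 4.A, Overview, gives a single primary objective covering both: whether oxytocin improves couples' "conflict resolution skills and mitigates their subjective, physiological, and neuroendocrine responses to this common stressor".
- Section 6, Data and Safety Monitoring Plan, Summary of the Protocol, agrees with 4.A: "The primary outcome in this study includes an improvement in conflict resolution skills and a reduction in subjective, physiological, and neuroendocrine reactivity to dyadic conflict". Yet the sentence just before it gives the aim as "initial feasibility and efficacy testing of oxytocin for the improvement of couples' conflict resolution skills", with no mention of reactivity.

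The next part of the monitoring plan says "A data analytic plan is outlined in the Data Analysis section". Section 4.G lists Hypothesis 1 (skills) and Hypothesis 2 (reactivity) without calling either primary. It applies 0.05 to all analyses and gives no testing order.

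The skills score is described in ways that do not match. The Laboratory Conflict Resolution Task text in section 4.D assigns each speaking turn one of ten codes. It mentions the total positive and total negative proportions only as a further possibility, and does not say which codes belong to which total. The monitoring plan instead lists among the main outcomes "the frequency and severity of negative conflict resolution skills and the frequency and intensity of positive conflict resolution skills".

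**The concern.** Reactivity cannot be both secondary and primary. A significant result on cortisol, say, would be a secondary finding under section 1 and could be reported as a primary one under sections 4.A and 6. Nothing in 4.G would rule out either report.

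Following section 1 alone does not close the gap. The positive total, the negative total or a single code could each be presented as the skills result, and either total could change with the way codes are allotted to it. The monitoring plan's severity and intensity add further candidates, for which the protocol describes no rating.

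**Working it through.** **Which text governs.** The documents give no error-rate or power figure to reproduce, so the first step is to compare the text.

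| Place | Skills | Reactivity |
|---|---|---|
| Section 1 | primary | secondary |
| Section 4.A | primary | primary |
| Section 6, Summary of the Protocol | primary | primary |
| Section 4.G | Hypothesis 1, unranked | Hypothesis 2, unranked |

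**How many outcomes could compete.**

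- Skills: two, the positive and negative proportions (section 4.D).
- Reactivity: eight (Specific Aim 2). These are craving, distress, feelings toward partner, heart rate, skin conductance, skin temperature, cortisol and DHEA. With the two skills totals, 2 + 8 = 10.
- Adding mood (Laboratory Task Timeline) and the single constructive-discussion item (Table 1) gives 12.
- Relationship satisfaction and aggression are not counted. In the timeline they appear only at 9:40am, before the spray at 9:50am, so as scheduled they have no post-dose value.

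These counts take one test per outcome. They do not multiply by partner or by time point.

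**Chance of at least one false positive.** Assumptions: two-sided tests at 0.05 (the plan does not state sidedness), no true effects, normal test statistics with a common correlation ρ, and any one significant result being enough. For ρ = 0 the chance is 1 − 0.95^k:

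- k = 2: 1 − 0.9025 = 0.0975
- k = 10: 1 − 0.5987 = 0.401
- k = 12: 1 − 0.5404 = 0.460

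For ρ > 0, with c = 1.96, it is 1 − ∫ φ(u) [Φ((c − √ρ·u)/√(1−ρ)) − Φ((−c − √ρ·u)/√(1−ρ))]^k du, evaluated numerically.

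| k | ρ = 0 | 0.5 | 0.9 |
|---|---|---|---|
| 2 (skills totals) | 9.75% | 9.1% | 7.0% |
| 10 | 40% | 29% | 13% |
| 12 | 46% | 32% | 13% |

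With one fixed primary score, k = 1 and the level is 5%.

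**If both must succeed.** For two tests, P(both significant) = 0.05 + 0.05 − P(at least one). At ρ = 0 this is 0.10 − 0.0975 = 0.0025. At ρ = 0.9 it is 0.10 − 0.0704 = 0.0296. The range is 0.25% to 3.0%, below 5% throughout.

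The cost is power. Assume 18 couples per arm (the 36 couples of section 4.B, split equally) and a couple-level standardised difference of 0.8. One test then has power Φ(0.8·√(18/2) − 1.96) = Φ(0.44) = 0.67. Requiring two such results gives 0.67 × 0.67 = 0.45 if they are independent, and at most 0.67 if they move together.

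**The case against.** The strongest reply is that section 1 is the formal statement of aims and the only place that uses both ranks. The order of the aims there and of the hypotheses in 4.G agrees with it. Sections 4.A and 6 can be read as condensed restatements. The study also calls itself preliminary and says so about its outcomes: "Because this study is a preliminary test of a new medication, we are interested in examining a broad range of outcome variables". All of this is fair. It supports choosing section 1 as the text to follow, and it makes this mainly a matter of reconciling wording. It does not remove the conflict, because sections 4.A and 6 attach the word primary to reactivity rather than calling it exploratory. A preliminary study can examine many outcomes and still say which one carries the claim.

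A second reply is that the monitoring plan joins skills and reactivity with *and*, so that both would have to succeed. On that reading there is no inflation, and this stands. But the sentence is not written as a success rule, and no such rule appears elsewhere.

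A reader might go further and infer that the plan accepts any one significant result, and so carries a false-positive rate of 40% or more. The documents do not support that: no section says one result suffices, and 40% needs ten independent outcomes. Nor is the skills outcome wholly unspecified, since the coding system and the comparison of Task 1 with Task 2 are both given. What is open is the summary score. The allotment of codes to positive and negative may be in the cited coding reference, so the point is limited to its not being stated here.

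**Conclusion.** The point holds. The status of reactivity is contradictory in current text, the Data Analysis section does not resolve it, and the skills score is not fixed even if section 1 governs. The established defect is that the primary claim is left open. The percentages illustrate one consequence and are not properties of the plan. They rest on assumed correlations and, for the inflated cases, on a success rule that the plan does not state. On those terms the false-positive chance is 7.0% to 9.75% for two skills totals, 13% to 40% for ten outcomes and 13% to 46% for twelve. Under the both-must-succeed reading it is 0.25% to 3.0% for two tests, with reduced power. The correction should be made before unblinding; participant safety is not affected.

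**What to change.** Before unblinding:

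1. Align section 4.A and the Data and Safety Monitoring Plan with section 1: skills primary, reactivity secondary or exploratory. Co-primary outcomes with a stated success rule would also cure the conflict, but would depart from section 1.
2. Name one primary skills score from section 4.D, either the total negative or the total positive proportion (the sponsor's choice), with the other as first secondary.
3. List which of the ten codes count as positive, negative or neither.
4. State in section 4.G the one treatment contrast from the dyadic multilevel model that is tested at 0.05.
5. Define severity and intensity, or delete them.

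The cost is rewording in sections 4.A, 4.D, 4.G and 6. No new data are needed if the proportions are used and severity and intensity are deleted; defining them may need extra coding. The downside for the sponsor is that significant reactivity results, and the proportion not chosen, can no longer be called primary.
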